16.2 SAFETY AND OTHER EVALUATIONS

This section specifies analyses related to COVID-19 pandemic from the following aspects:

- COVID-19 Status
- Disposition
- Demographics and Other Baseline Characteristics
- Study visit (missing entire visit due to COVID-19 or missing assessments due to COVID-19)
- Protocol deviation
- Study drug interruption(s) due to COVID-19
- TEAEs related to COVID-19 infection

Safety Population will be used for the planned analyses in this section described above, unless stated otherwise.

The number of participants impacted by COVID-19 during the study and COVID-19 status will be summarized by treatment group. In addition, the number of participants impacted by COVID-19 and their corresponding disposition status in the double-blind treatment period and the follow-up period will be summarized respectively.

Baseline characteristics (including demographic, baseline disease characteristics, and relevant medical history) will be summarized relative to the onset of pandemic (date of randomization \leq Mar 11, 2020 vs. date of randomization $>$ Mar 11, 2020).

The number of participants who missed at least one entire visit due to COVID-19 will be summarized by treatment group. Furthermore, the number of participants who missed at least one assessment due to COVID-19 will be summarized by assessment category (laboratory, vital signs, ECG, C-SSRS, YMRS, EPS scales) and by visit.

The number of participants with significant protocol deviation due to COVID-19 will be provided. The number of participants with any COVID-19 related treatment interruption(s) will be provided as well.

The number of participants with TEAEs related to COVID-19 infection will be provided.

Supporting listings for the above described analyses will be provided. Furthermore, a listing of TEAEs leading to study discontinuation related to COVID-19 will be provided.

17.0 **CHANGES TO ANALYSES SPECIFIED IN PROTOCOL**

In Section 11.0 (Health Outcome Analyses), the term “Study center” in the ANCOVA model for analyzing PCS-12 and MCS-12 will be replaced with terms country and ADT failure category to align with the analyses for other efficacy endpoints.

In Section 10.1 (Adverse Events), AE summary timeframe was modified to align with AE reporting period specified in the protocol amendment 1. The new time frame is defined below:

An AE that occurs more than 30 days after the date of the last dose of DB IP or occurs after the last safety follow-up visit (whichever comes last) will not be summarized except for AEs related to reported pregnancies. AEs associated with pregnancies reported in the protocol-required timeframe up to approximately 12 weeks following the last dose of DB IP, will be summarized.

The summary of SAEs was modified in Section 10.1. The definition of on-therapy SAE was updated to TESAE, and summary timeframe will align with general AE summary timeframe as specified above.

18.0

APPENDICES

Appendix I Pattern-Mixture Model Details

For repeated measures with the monotone missing mechanism, the pattern-mixture model with non-future dependent missing assumption, proposed by [Kenward et al. \(2003\)](#), provides a feasible solution to accommodate certain missing not at random (MNAR) mechanism. The methodology relies on constructing unidentifiable conditional densities using identifiable densities and borrows techniques from standard multiple imputation.

1. Non-Future Dependent Missing Assumption

Assume there are T designed visits in a longitudinal study and let $y_i (i = 1, 2, \dots, T)$ represent participant's measurement at Visit i. When the missing mechanism is monotone, the pattern of missing data can be defined by the number of measurements (L) actually observed from the participant. Let $f(y_i, \dots, y_j | L = t)$ denote the conditional density of y_i, \dots, y_j , given that the last observed measurement is at Visit t. Then the overall density function for Pattern t can be written as

$$f(y_1, \dots, y_T | L = t) = f(y_1, \dots, y_t | L = t) f(y_{t+1} | y_1, \dots, y_t, L = t) \times \prod_{s=t+2}^T f(y_s | y_1, \dots, y_{s-1}, L = t) \quad (1)$$

Note on the right hand side of (1) the first factor is clearly identifiable from the observed data, while the second and the beyond are not, due to lack of available data. The second factor $f(y_{t+1} | y_1, \dots, y_t, L = t)$ could be identifiable based on an assumed relationship between $f(y_{t+1} | y_1, \dots, y_t, L = t)$ and $f(y_{t+1} | y_1, \dots, y_t, L \geq t + 1)$. The third and beyond factors $f(y_s | y_1, \dots, y_{s-1}, L = t)$ (with all $s \geq t + 2$) could be identifiable with the help of non-future dependent missing assumption.

For longitudinal data with dropouts, non-future dependent missing (NFD) mechanism ([Kenward et al., 2003](#)) assumes that the unidentifiable conditional distributions of $y_s (s \geq t + 2)$, given earlier measurements, in Pattern t, is equal to the corresponding distribution in patterns $L \geq s - 1$:

$$f(y_s | y_1, \dots, y_{s-1}, L = t) = f(y_s | y_1, \dots, y_{s-1}, L \geq s - 1) \quad (2)$$

The right hand side of (2) can further be partitioned into

$$f(y_s | y_1, \dots, y_{s-1}, L \geq s-1) = \sum_{j=s-1}^T \omega_{s-1,j} \cdot f(y_s | y_1, \dots, y_{s-1}, L = j) \quad (3)$$

Where mixture probabilities $\omega_{s-1,j}$ are:

$$\omega_{s-1,j} = \frac{\alpha_j f(y_1, \dots, y_{s-1} | L = j)}{\sum_{t=s-1}^T \alpha_t f(y_1, \dots, y_{s-1} | L = t)}, \text{ and } \alpha_j \text{ represents the fraction of} \quad (4)$$

participants from Pattern j.

Each factor of the unidentifiable conditional distribution of y_s ($s \geq t + 2$) on the right side of (1) can be expressed using the following:

- $f(y_s | y_1, \dots, y_{s-1}, L = s-1)$, the unidentifiable conditional distribution of the first missing in pattern $s-1$,
- $f(y_s | y_1, \dots, y_{s-1}, L = j)$, the identifiable conditional distributions of y_s given y_1, \dots, y_{s-1} of pattern j ($j \geq s$), and
- α_j , the fraction of participants from pattern j ($j \geq s-1$).

So under NFD, all the unidentifiable conditional distribution on the right side of (1) can be estimated and missing value could be therefore imputed based on the assumption for unidentifiable conditional distribution of the first missing.

We re-formulate the partition in (3), for $s \geq t+2$, as the following:

$$f(y_s | y_1, \dots, y_{s-1}, L = t) = \delta_{s-1} f(y_s | y_1, \dots, y_{s-1}, L = s-1) + (1 - \delta_{s-1}) f(y_s | y_1, \dots, y_{s-1}, L \geq s) \quad (5)$$

for $s \geq t+2$ with $\delta_{s-1} = \omega_{s-1,s-1}$.

Therefore, under monotone missing and NFD assumption, the unidentifiable conditional densities for Visit s in Pattern t ($s \geq t + 2$) can be expressed as a mixture distribution of $f(y_s | y_1, \dots, y_{s-1}, L = s - 1)$ - the unidentifiable conditional distribution of the first missing measurement y_s in Pattern $s - 1$, and $f(y_s | y_1, \dots, y_{s-1}, L \geq s)$ - the identifiable conditional distribution of y_s from all the patterns with observed data at Visit s or beyond:

$$f(y_s | y_1, \dots, y_{s-1}, L \geq s) = \sum_{j=s}^T \lambda_{s-1,j} f(y_s | y_1, \dots, y_{s-1}, L = j) \quad (6)$$

where the mixture probability $\lambda_{s-1} = \omega_{s-1,j} / (1 - \omega_{s-1, s-1}) =$

$$\frac{\alpha_j f(y_1, \dots, y_{s-1} | L = j)}{\sum_{t=s}^T \alpha_t f(y_1, \dots, y_{s-1} | L = t)} \text{ for } j \geq s, \text{ where } \alpha_j \text{ is the fraction of} \quad (7)$$

participants from Pattern j .

The conditional densities for the first missing are selected as:

$$f(y_s | y_1, \dots, y_{s-1}, L = s - 1) = f(y_s - \Delta | y_1, \dots, y_{s-1}, L \geq s) \text{ for } s = 2, \dots, T \quad (8)$$

Note that the two distributions only differ by a shift (Δ) parameter. When $\Delta = 0$, the missing value y_s in Pattern $s-1$ is imputed based on the distribution of all observed data up to Visit s , as a result, leading to missing at random (MAR) missingness. When $\Delta \neq 0$, (8) will introduce a scenario of MNAR. The similar idea was also presented in the recent publication “The Prevention and Treatment of Missing Data in Clinical Trials” by the National Academies Press. The selection of the plausible values for the shift parameter (Δ) is discussed in Section 3.0.

Note that per recommendation in Wang and Daniels (2011), only the observed data within pattern is assumed to be multivariate normal. The observed data distribution can be expressed in terms of the marginal distribution of baseline measurement and the conditional distributions of postbaseline measurements given earlier measurements. Assuming that these distributions are normal, the linear regression of each observation on prior observations will yield least-squares estimates of model parameters that can be utilized for independent posterior draws of model parameters for observed data. Multiple imputation approach will be used to estimate the overall mean at the final time point.

2. Imputation Procedure

All the missing data will be imputed to create complete datasets, then statistical analysis can be performed using appropriate techniques such as ANCOVA. The imputation can accommodate MNAR missing data mechanisms, based on the theory discussed in the previous section.

The model parameters for each dropout pattern, ie, the mean, variance and proportions of observations in each pattern, are drawn from their posterior distributions prior to the imputation of missing data for a single imputation.

The details of imputation within a pattern, say Pattern t , are as the following:

Step 1. Impute the first missing value y_{t+1} for each participant in Pattern t ($t = 1, \dots, T - 1$):

- a. Compute estimates of mixture probabilities $\lambda_{s-1,j}$ in (7) with $s = t+1$ given the posterior draw of proportions of observations in each pattern and the posterior draw of regression parameters for the observed data.
- b. Draw a random integer from $\{s, \dots, T\}$ to index a component distribution on the right hand side of (6), using mixture probabilities obtained in a). Draw y_{t+1}^* from the identified component normal distribution. Impute the missing y_{t+1} as $\tilde{y}_{t+1} = y_{t+1}^* + \Delta$.

Step 2. Impute the rest of the missing values of $y_{t+2}, y_{t+3}, \dots, y_T$ for participants in Pattern t :

Starting with imputation for y_{t+2} , first, similar to Step 1, draw y_{t+2}^* from the normal mixture (6) based on the observed y_1, \dots, y_t and the already imputed \tilde{y}_{t+1} for the participant. Then the missing y_{t+2} is imputed as $\tilde{y}_{t+2} = y_{t+2}^* + \Delta$ with probability δ_{t+1} and as $\tilde{y}_{t+2} = y_{t+2}^*$ with probability $1 - \delta_{t+1}$, where the mixture probability $\delta_{t+1} = \omega_{t+1,t+1}$ is obtained from (4) given the posterior draw of proportions of observations in each pattern and the posterior draw of regression parameters for the observed data.

Missing values of y_{t+3} through y_T can be imputed similarly as y_{t+2} .

To summarize, the imputations of y_{t+1} through y_T is done recursively within each Pattern t (for all $t = 1, \dots, T - 1$) to create a complete dataset after imputation is done for all patterns with missing values.

The above imputation procedure is applied to all participants in each missing data pattern to create a single imputed data set. Repeating the process of drawing parameters from the posterior distribution and imputing missing data given the posterior draw m times will yield m imputed data sets. The observed or imputed values at the final data point are averaged to obtain the overall mean estimate for each imputed data set, and the multiple imputation estimate is obtained by averaging the estimates across m imputations.

In this sensitivity analysis, m is set to equal to 200.

3. Determination of the Shift Parameter Values

The common shift parameter Δ is the difference between the mean of y_{t+1} among those who drop out at Visit t and those who remain beyond Visit t ($1 \leq t \leq T - 1$). The exact value of Δ is unknown and can't be estimated from data because of missingness. The magnitude of Δ depends on the medical aspects of the trial. Using relevant historical data, one may select Δ as a proportion of the sample standard deviation or a proportion of observed treatment efficacy.

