8.8 Early Discontinuation of Patients

Patients may discontinue from the study at any time for any reason. Discontinuation is permanent; once a patient is discontinued, he/she shall not be allowed to enroll again.

Patients can be prematurely discontinued from the study and subsequently enter the safety follow-up period for one of the following reasons:

- AE
- Noncompliance with protocol
- Noncompliance with IP dosing regimen and/or ongoing ADT dosing regimen
- Withdrawal of consent (a clear reason must be documented when possible)
- Patient decision to not continue in the study
- Lost to follow-up (every effort must be made to contact the patient; a certified/traceable letter must be sent)
- Study terminated by Sponsor
- Site terminated by Sponsor
- Pregnancy
- Other reasons

Notification of early patient discontinuation from the study and the reason for discontinuation will be clearly documented on the appropriate eCRF page. Patients who take IP during the study and who prematurely discontinue from the study, regardless of cause, should be seen for a final assessment. A final assessment will be defined as completion of the evaluations scheduled for Visit 6/ET. If the patient discontinues after IP is taken, the patient is also expected to return for the Safety Follow-up Visit (Visit 7) 4 weeks after completion of the ET Visit.

At a minimum, the following information should be collected when a patient is discontinued:

1. The reason the patient discontinued
2. The date of the last dose of IP taken by the patient. All IP should also be retrieved from the patient.
3. The date of the last study assessment and/or contact. A follow-up contact (telephone or visit) will be arranged as appropriate

4. (S)AEs

5. Compliance with the IP administration as specified in this protocol

6. Final Assessments: Unless there is withdrawal of consent, every effort should be made to ensure that all procedures and evaluations scheduled for Visit 6/ET and subsequently Visit 7 (Safety Follow-up Visit) are performed ([Table 1](#), and Section [8.4](#)).

Discontinued patients will not be replaced, and re-screening will not be allowed.

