The analysis will be performed based on all postbaseline scores using only the observed cases without imputation of missing values. The treatment difference in the primary endpoint at Week 6 for each active treatment group versus placebo in the mITT population will be estimated and reported along with the corresponding 95% CI and the p-value.

The two-stage mixture parallel gatekeeping procedure (Dmitrienko 2011) (truncated Hochberg with truncation parameter of 0.9 for the primary endpoint and regular Hochberg for the secondary endpoint) will be used to control the overall type I error rate at a 0.025 level (1-sided) for multiple comparisons of 2 active doses with placebo for the primary endpoint and key secondary endpoint. Details are provided in Section 9.2.

The study will be considered positive if at least 1 dose arm of cariprazine is statistically superior to placebo for change from baseline in MADRS total score at Week 6 after multiplicity adjustment.

A sensitivity analysis using a pattern-mixture model based on non–future-dependent missing value restrictions (Kenward et al, 2003) will be performed to assess the robustness of the primary MMRM results to the possible violation of the missing-at-random assumption. The details of this sensitivity analyses are as follows:

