The pattern for the pattern-mixture model will be defined by the participant’s last visit with an observed value. The observed MADRS total score at a visit is assumed to have a linear relationship with the participant’s prior measurements. The missing values will be imputed under the assumption that the distribution of a missing observation differs from the observed only by a shift parameter value Δ . The dataset with missing values imputed will be analyzed using an analysis-of-covariance (ANCOVA) model with treatment group, pooled country, and ADT failure category (per CRF), as factors and baseline MADRS total score as a covariate for between–treatment-group comparison at Week 6. The imputation of missing values and the analysis will be performed multiple times, and the inference of this sensitivity analysis will be based on the combined estimates using the standard multiple imputation technique. The values for Δ will be selected as 0 to 6, inclusively. This range is selected because the mean reduction of MADRS score from baseline within a treatment group at Week 6 is likely to be within 15 points (Durgam et al, 2016; El-Khalili et al, 2010), and a Δ value of 6 accounts for 40% of treatment efficacy.

The second sensitivity analysis will consider dropout reasons while imputing missing values after the discontinuation. Participants who discontinued due to lack of efficacy in the cariprazine arms are assumed to have no treatment effect after the discontinuation. These participants are assumed to copy the profile of placebo arm and missing values are imputed based on the distribution estimated from the placebo group using copy-reference approach (Carpenter et al, 2013). The rest of missing values in the placebo arm and cariprazine arms will be imputed using the observed data in their respective group under the MAR assumption.

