The study will randomize approximately 750 participants in a 1:1:1 ratio to cariprazine 1.5mg/day, cariprazine 3mg/day, and placebo groups. A sample size of 250 participants per arm will provide approximately 83% statistical power to show statistically significantly higher effect in each dose of cariprazine versus placebo based on the mITT analysis set. The study has approximately 90% statistical power to show that at least 1 of the 2 cariprazine doses is statistically significantly more efficacious than placebo in the primary endpoint. These calculations assumed an effect size of 0.286. All statistical powers presented in this section were calculated adjusting for multiple comparisons across the two cariprazine doses and the primary and secondary endpoints using the Hochberg-based gatekeeping procedure with re-testing with the family-wise type I error rate being controlled at a 0.05 level (2-sided). The dropout rate is assumed to be 15% at Week 6. Within-person correlation for the primary endpoint is assumed to be 0.58. This value is used in the sample size calculation to calculate an inflation factor that accounts for information loss due to the missing data at Week 6 for longitudinal data collection.

Assumptions of effect size, intracorrelation and dropout rate are based on cariprazine Study RGH-MD-75.

14.0 **STATISTICAL SOFTWARE**

Statistical analyses will be performed using version 9.4 (or newer) of SAS on a Linux operating system.

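### The pattern-mixture analysis shifts every arm by the same Δ, so it barely tests the cariprazine–placebo difference when dropout is similar across arms

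*SAP*

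**What the plan says.** SAP 9.1 gives the purpose of the first sensitivity analysis as "to assess the robustness of the primary MMRM results to the possible violation of the missing-at-random assumption". Missing values are imputed with a shift, and "The values for Δ will be selected as 0 to 6, inclusively"; Protocol 7.3.1 has the same range. The completed data go into an ANCOVA comparing groups at Week 6.

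Appendix I, Section 3 begins its definition with "The common shift parameter Δ is the difference between the mean of", contrasting the next value in those who drop out with that in those who remain. Equation (8) and imputation Steps 1 and 2 carry no treatment index. Section 2 closes with: "The above imputation procedure is applied to all participants in each missing data pattern to create a single imputed data set". Neither document has an arm-specific Δ, a run with placebo held at Δ = 0, or a tipping-point search.

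The second sensitivity analysis in SAP 9.1 is arm-specific but narrow: "Participants who discontinued due to lack of efficacy in the cariprazine arms are assumed to have no treatment effect after the discontinuation". These participants are imputed from the placebo profile. All other missing values "will be imputed using the observed data in their respective group under the MAR assumption". The COVID-19 variant in SAP 16.1 has the same limit.

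**The concern.** The departure from MAR that could overturn a positive result is cariprazine dropouts faring worse than MAR predicts, relative to placebo dropouts. Adding the same amount to both arms does not create that contrast. With matched dropout the shift subtracts out. With unmatched dropout the answer depends on which arm lost more patients, or lost them later, rather than on how cariprazine dropouts are assumed to fare.

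Copy-reference creates the contrast for one dropout reason only. Cariprazine patients who leave because of adverse events stay MAR in their own arm. A claim that the result is robust to data not missing at random could therefore rest largely on a scenario that cancels by construction.

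**Working it through.** **Inputs.** Δ of 0 to 6 (SAP 9.1, Protocol 7.3.1). Correlation ρ = 0.58, dropout 15% (one rate, not by arm), effect size 0.286 and 250 per arm (SAP 13.0). Assumed: compound symmetry, baseline among the predictors, regressions fitted by arm, dropout unrelated to the scores, and equal thirds of dropout after Weeks 1, 2 and 4. The SD is not in the documents; I use 8.5 to 10.

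**The plan's own figures.** The range for Δ is justified as 6/15 = 40%, a share of the reduction within a group, not of the difference between groups. Power reproduces: inflation (1 − 0.58² × 0.15)/(1 − 0.15) = 1.117, so 250/1.117 = 223.8 effective patients per arm. Hochberg then gives 83.9% per dose and 91.0% for at least one (Protocol 7.7: 84% and 90%). The truncated version with γ = 0.9 gives 83.5% and 90.9% (SAP 13.0: 83% and 90%).

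**Shift in one arm at Δ = 6, 5% dropout after each of three visits.** The slope on each of k prior values is ρ/(1 + (k − 1)ρ): 0.58/2.16 = 0.2685 for k = 3 and 0.58/2.74 = 0.2117 for k = 4. The Step 2 probability of a further shift is 0.05/0.95 = 0.0526 at Week 4 and 0.05/0.90 = 0.0556 at Week 6.

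- Last seen Week 4: Week 6 shift = 6.00.
- Last seen Week 2: Week 4 shift = 6; Week 6 shift = 0.2117 × 6 + 0.0556 × 6 = 1.60.
- Last seen Week 1: Week 2 shift = 6; Week 4 shift = 0.2685 × 6 + 0.0526 × 6 = 1.93; Week 6 shift = 0.2117 × (6 + 1.93) + 0.0556 × 6 = 2.01.

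Arm mean shift = 0.05 × (6.00 + 1.60 + 2.01) = 0.48 points. The same steps give 0.31 at 10% dropout and 0.66 at 20%. For 15% they give 0.24 if all drop out after Week 1 and 0.90 (0.15 × 6) if all drop out after Week 4.

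| Dropout, cariprazine / placebo | Δ = 6 applied to | Shift, cariprazine | Shift, placebo | Change in difference |
|---|---|---|---|---|
| 15% / 15%, even | both | 0.48 | 0.48 | 0.00 |
| 15% / 15%, even | cariprazine only | 0.48 | 0 | 0.48 against |
| 15% / 15%, all after Week 4 | cariprazine only | 0.90 | 0 | 0.90 against |
| 20% / 10%, even | both | 0.66 | 0.31 | 0.35 against |
| 10% / 20%, even | both | 0.31 | 0.66 | 0.35 in favour |
| 15% after Week 1 / 15% after Week 4 | both | 0.24 | 0.90 | 0.66 in favour |

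These shifts do not depend on the SD. Without baseline as a predictor, 0.48 becomes 0.53; correlations of 0.4 to 0.7 give 0.46 to 0.49.

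**Size against the planned effect.** 0.286 × 8.5 = 2.43 and 0.286 × 10 = 2.86 points; 0.48/2.86 = 17% and 0.48/2.43 = 20%.

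**Simulation of the Appendix I procedure.** Two simulations with different assumed SDs agree on the pattern.

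- SD 9, 200,000 per arm, 15% dropout in both arms with the same timing: the difference is −2.57 at Δ = 0, −2.58 at common Δ = 6 and −2.05 at cariprazine-only Δ = 6. With equal totals but earlier cariprazine dropout, common Δ = 6 moves it from −2.53 to −2.92, in favour of cariprazine.
- SD 9.5, 250 per arm, 350 trials, 15 imputations, nominal pairwise 0.05: mean z is −3.64 at Δ = 0, −3.55 at common Δ = 6 and −2.96 at cariprazine-only Δ = 6. Of trials significant at Δ = 0, 2% lose significance under the common shift and 13% under the cariprazine-only shift. With a true effect of 0.20 SD the losses are 7% and 33%.

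**Pooled imputation.** The documents do not say whether the regressions are fitted by arm. If pooled, the first simulation gives −2.33 at both Δ = 0 and common Δ = 6. The shift still cancels, and the Δ = 0 run no longer matches the −2.57 from by-arm imputation.

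**The case against.** The documents never state outright that Δ is the same in all arms. The word common could mean common over visits and dropout patterns, and Appendix I has no treatment index on any quantity. That is fair as to wording, but the procedure covers all participants, only one list of values is given, and no passage points to an arm-specific Δ.

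The plan has other checks: copy-reference, an LOCF ANCOVA covering every dropout reason, and time-course plots by dropout reason. Copy-reference is a real arm-specific departure from MAR, limited to one reason. LOCF is planned for comparison with historic studies and does not test a chosen disadvantage for cariprazine dropouts.

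Lack of efficacy is not named among the discontinuation reasons in Protocol 8.8. The case report form, not available here, may record it, so the conclusion places no weight on this.

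The strongest objection is materiality. At the planned effect, a cariprazine-only shift costs 2.72 − 2.23 = 0.49 points over Δ = 6. With an SE near 0.75, the average trial loses nominal significance only at about (2.72 − 1.96 × 0.75)/(0.49/6) = 15. This stands: a trial that meets its planned effect is fairly robust. A weaker result is not. At a true effect of 0.20 SD, mean z falls from −2.60 to −1.93 at cariprazine-only Δ = 6, but only to −2.52 at common Δ = 6. The 0.66-point timing case is a bound, not an expectation.

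**Conclusion.** The concern holds. As specified, the Δ analysis leaves the Week 6 difference essentially unchanged when dropout matches in amount and timing, and otherwise moves it in a direction set by the imbalance. At Δ = 6 with 15% dropout spread evenly, the untested erosion is 0.48 points, or 17–20% of the planned effect (0.90 points if all dropout falls just before Week 6). The point values rest on the assumed correlation structure and dropout timing; the percentages also rest on the assumed SD.

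Cancellation concerns the estimate. The SE still rises by about 1.7% at common Δ = 6 (0.748 to 0.761), so p-values move slightly. This is a supportive analysis: the primary test, its error control and its power are unaffected. The change is worth making because it is cheap and makes the analysis serve its stated purpose.

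**What to change.** In SAP 9.1 and Appendix I, Sections 2 and 3, add text such as: *Missing values in the cariprazine arms will be imputed with shift Δ and those in the placebo arm with shift 0, using imputation regressions fitted by treatment arm. Δ will run from 0 to 6 and beyond, until the comparison with placebo is no longer significant under the primary-endpoint step of the multiplicity procedure in Section 9.2. The tipping-point Δ will be reported for each dose.*

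Varying Δ separately in each arm over a grid is an acceptable alternative. Also state the step in Δ, an upper limit, and that no tipping point is reported for a dose not significant at Δ = 0. The SAP's own 15-point within-group reduction is a natural upper limit. Keep the common-Δ run as a supplement.

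The cost is a short SAP edit, one arm condition in the imputation program and extra runs for Δ above 6. The downside for the sponsor is less favourable sensitivity estimates. Data collection and the primary test do not change.
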